10.2 SECONDARY ENDPOINTS

The secondary endpoints were:

❖ HbA1c:

- Value measured in the laboratory from a blood sample taken before the D0 visit and just before the 3-month visit

❖ Glucose Level Measurements

- Average Glucose Measurements over each period and over the entire study duration
- Minimum and maximum values
- Time in range expressed as a % (see ADA and International Consensus on Time in Range recommendations^{25,26})

These values are automatically calculated by the FreeStyle Libre software and will be reported by the investigator.

❖ Glycemic events

- Number of symptomatic and non-symptomatic hypoglycemic episodes during the evaluation period, broken down by severity level (see below)

- Number of symptomatic and non-symptomatic hyperglycemia events during the evaluation period, broken down by severity level (see below)

This information is derived from the FreeStyle Libre data and the data entered by the patient in the PDM.

The definition of hypoglycemia and hyperglycemia is the ADA consensus definition²⁵ :

Outcome	Definition
Hypoglycemia	Level 1: glucose <70 mg/dL (3.9 mmol/L) and glucose \geq 54 mg/dL (3.0 mmol/L) Level 2: glucose <54 mg/dL (3.0 mmol/L) Level 3: a severe event characterized by altered mental and/or physical status requiring assistance
Hyperglycemia	Level 1—elevated glucose: glucose >180 mg/dL (10 mmol/L) and glucose \leq 250 mg/dL (13.9 mmol/L) Level 2—very elevated glucose: glucose >250 mg/dL (13.9 mmol/L)
Time in range	Percentage of readings in the range of 70–180 mg/dL (3.9–10.0 mmol/L) per unit of time

❖ Device tolerance

- Local skin tolerance at the pump site (adhesive hold) and at the FreeStyle Libre blood glucose sensor site (adhesive hold).
- Any local or systemic safety issues should be reported during the study, including the additional one-month phase at the end of the study for patients in the "OmniPod" group

❖ Incidents with devices

- Any type of incident involving the operation of the medical devices used, particularly for pumps: removal, control problems, transmission difficulties, obstructions, leaks, etc.

❖ Patient satisfaction

- Self-questionnaire evaluating satisfaction with the use of the device (pump+PDM)
- Final question regarding patient preference between the Medtrum device and the Insulet device

❖ Insulin treatment

- The insulin treatment used should be documented
- Delivered insulin doses will be derived from the pump's data logging

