11.2.4 Analysis of the effectiveness / performance of the device

Analysis of primary efficacy endpoint:

The non-inferiority analysis of the primary efficacy endpoint will be performed with an ANOVA, with the DM as an explanatory variable, on the *per protocol* population and then on the *intention-to-treat* population. If the upper bound of the IC95% of the Omnipod-Medtrum estimated difference in means (LSmeans) exceeds the non-inferiority bound, it will be rejected.

Non-inferiority bounds are defined in this protocol and will be used in the statistical analysis plan.

If non-inferiority is demonstrated, a superiority analysis will be conducted.

Secondary efficacy endpoint analyses:

The secondary efficacy endpoints will be analyzed for the variables listed below.

Each variable will be described globally and by pump group.

In case of non-inferiority analysis, the same methodology as for the primary endpoint will be used.

In case of comparison of quantitative variables, parametric (T-test) or non-parametric (Mann-Whitney) tests of comparison of means will be used. In case of comparison of qualitative variables, CHI² or Fisher exact tests will be used.

In case of tests on changes within each group, paired data tests will be used (paired data T-test or Wilcoxon signed ranks test, depending on the distribution of the data).

❖ **HbA1c:**

- Evolution of the value measured in the laboratory from a blood sample taken before the D0 visit and just before the 3-month visit
- Description in the total population, in each group and comparison between groups.

❖ **Glucose measurements**

- Average of glucose measurements over each period and over the entire study duration
- Description of the minimum and maximum values over the total duration of the study
- Description of the % of Time in Range (see ADA and International Consensus on Time in Range recommendations^{25,26})
- Description in the total population, in each group and comparison between groups.

❖ **Glycemic events**

- Description of the number of symptomatic and non-symptomatic hypoglycemic events during the evaluation period, broken down by severity level (see ADA consensus definitions²⁵)
- Description of the number of symptomatic and non-symptomatic hyperglycemia events during the evaluation period, broken down by severity level (see ADA consensus definitions²⁵)
- Description in the total population, in each group and comparison between groups.
-

❖ **Device tolerance**

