4.4.2 Secondary endpoints

The secondary endpoints were:

- HbA1c:
 - Value measured in the laboratory from a blood sample taken before the D0 visit and just before the 3-month visit
- Glucose Level Measurements
 - Average of glucose measurements over each time period and over the entire study duration
 - Minimum and maximum values
 - Time in range expressed as a %.

These values were automatically calculated by the FreeStyle Libre software and will be reported by the investigator.

- Glycemic events
 - Number of symptomatic and non-symptomatic hypoglycemic events during the evaluation period, broken down by severity level
 - Number of symptomatic and non-symptomatic hyperglycemia events over the evaluation period, broken down by severity level

This information was derived from the Free Freestyle data and the data entered by the patient in the MDP.

The definition of hypoglycemia and hyperglycemia is the ADA consensus definition:

Table 1—Summary of consensus definitions			
Outcome	Definition		
Hypoglycemia	Level 1: glucose <70 mg/dL (3.9 mmol/L) and glucose \geq 54 mg/dL (3.0 mmol/L) Level 2: glucose <54 mg/dL (3.0 mmol/L) Level 3: a severe event characterized by altered mental and/or physical status requiring assistance		
Hyperglycemia	Level 1—elevated glucose: glucose $>$ 180 mg/dL (10 mmol/L) and glucose \leq 250 mg/dL (13.9 mmol/L) Level 2—very elevated glucose: glucose $>$ 250 mg/dL (13.9 mmol/L)		
Time in range	Percentage of readings in the range of 70–180 mg/dL (3.9–10.0 mmol/L) per unit of time		

- Device tolerance
 - Local skin tolerance at the pump site (adhesive hold) and at the FreeStyle Libre blood glucose sensor site (adhesive hold)
 - Any local or systemic safety issues were to be reported during the study, including the additional one-month phase at the end of the study for patients in the Omnipod group
- Incidents with devices
 - Any type of incident involving the operation of the medical devices used, especially for pumps: pulling out, control problems, transmission difficulties, occlusion, leakage, etc.
- Patient satisfaction
 - Self-questionnaire evaluating satisfaction with the use of the device (pump + PDM)

- Final question regarding patient preference between the Medtrum device and the Insulet device
- Insulin treatment
 - The insulin treatment used should be documented

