7.4 ANALYSIS OF THE EVALUATION CRITERIA

7.4.1 Primary endpoint analysis

The primary endpoint is the estimate of HbA1c at 3 months based on the mean of continuous glucose measurements obtained during the last 10 weeks of follow-up.

HbA1c estimation will be described by treatment group and then by type of diabetes.

The non-inferiority analysis of the primary efficacy endpoint will be performed with an ANCOVA, with the medical device as an explanatory variable and an adjustment on the estimate of HbA1c at Baseline, on the PP population.

If the upper bound of the IC95% of the Omnipod-Medtrum estimated difference in means (LSmeans) exceeds the non-inferiority bound set at 0.4, non-inferiority will not be demonstrated.

If non-inferiority is demonstrated, a superiority analysis will be conducted. If the upper bound of the IC95% of the estimated difference in mean is less than -0.3, superiority will be demonstrated.

The MIXED procedure (SAS® 9.4) will be used.

Code:

```
proc mixed data=XX order=data;
where PP = 1;
class DM;
model ESTIM_HBA1c = ESTIM_HBA1c_BASELINE DM;
lsmeans DM / diff=control cl;
run;
```

A sensitivity analysis will be performed on the ITTm population with imputation of missing data by the mean or median according to the distribution of the primary endpoint.

A subgroup analysis will be performed on the population of patients with an LSP wear rate >70% at M3.

Exploratory analysis:

Univariate analyses will be conducted on age in 2 classes (below or above the median), sex, type of diabetes, center, and duration of diabetes in 3 classes (<5 years; between 5 and 10 years; >10 years). If the p-value <0.05, the variable will be included in the full model. Then a top-down stepwise strategy will be conducted to select the variables for the final model.

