7.4.2 Secondary endpoint analyses

Analyses will be performed on the ITTm population.

Each variable will be described globally and by pump group.

The secondary endpoints are:

1. HbA1c

The evolution of HbA1c (measured in the laboratory) between D0 and 3M will be described, and a comparison between the groups will be made using a Student's t test or a Mann and Whitney test.

2. Glucose level measurement

The mean blood glucose level and its standard deviation (Blood Glucose Deviation SD) will be described over each period (between V1 and V2, then between V2 and v3, then between V3 and V4) and over the total duration of the study (mean, median, standard deviation, Q1-Q3, minimum and maximum). The coefficient of variation of glucose values will also be described.

The evolution of the average blood glucose level compared to baseline will be described at each visit.

FSL wear time (%) will be described.

The % of blood glucose values spent in target (time in range: [70; 180]), hypoglycemia (<70mg/dl), and hyperglycemia (>180 mg/dl) will be described over each time period in each pump group and in the total population.

For these criteria, comparisons between groups will be made using the Student or Mann-Whitney test.

3. Glycemic events

The number of hypoglycemic events will be described overall and in each period by severity level (according to ADA consensus definitions) overall and in each pump group.

Comparisons between groups will be made using Student or Mann-Whitney tests.

The % of time spent in hyperglycemia will be described overall and over each period and in each pump group. Comparisons between groups will be made using Student's t test or Mann and Whitney test.

4. Device tolerance

The analysis of this criterion is detailed in section 7.4 of this document.

5. Incidents with devices

The following criteria will be described for each period and by pump group (after reclassification):

- Pump occlusion (yes; no)
 - If yes, number of times
- Pump detachment (yes; no)
 - If yes, number of times
- Complete stop / breakage of the pump (yes; no)
 - If yes, number of times
- Other pump malfunction (yes; no)
 - All other possible malfunctions will be listed.

6. Patient satisfaction

The following criteria will be described for each period and by pump group:

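### SAP 7.4.2 sets no cut at V3 for its overall glycaemic comparisons, so the optional Omnipod-arm month on the Medtrum pump can be pooled into them

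*SAP*

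**What the plan says.** SAP 7.4.2 describes mean glucose over V1-V2, V2-V3, "then between V3 and V4) and over the total duration of the study". For glycaemic events it says "The number of hypoglycemic events will be described overall and in each period by severity level", and for hyperglycaemia "The % of time spent in hyperglycemia will be described overall and over each period". Each of these items is followed by a plan for Student or Mann-Whitney tests between groups. The test sentences name no window, and no rate per unit of time is planned for the event counts.

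The endpoint definition does not supply the window. SAP 4.4.2 has "Number of symptomatic and non-symptomatic hypoglycemic events during the evaluation period, broken down by severity level", and Protocol 10.2 and 11.2.4 use near-identical wording ("Number of symptomatic and non-symptomatic hypoglycemic episodes during the evaluation period, broken down by severity level"; "Description of the number of symptomatic and non-symptomatic hypoglycemic events during the evaluation period, broken down by severity level"). None of them defines the evaluation period.

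The extra month is optional (Protocol summary, duration of follow-up). It is open only to patients randomised to Omnipod and is spent on the Medtrum pump (Protocol 7.6). Glucose data and glycaemic events are collected in it (Protocol 7.2 and 7.6).

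Other windows are stated. Laboratory HbA1c in SAP 7.4.2 runs from D0 to 3 months, and the primary endpoint in SAP 7.4.1 is estimated HbA1c "at 3 months based on the mean of continuous glucose measurements obtained during the last 10 weeks of follow-up".

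**The concern.** A between-group comparison needs the same observation window in both arms, with each arm on its allocated pump. V3-V4 meets neither condition. It lengthens observation in one arm only, for a self-selected part of that arm, and the added time is on the other arm's device.

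Raw event counts are the sensitive case: more weeks of observation give more events whatever the pump does. The extra events would be counted against the comparator, in favour of the sponsor's pump. The comparison is more than descriptive, because the statistical analysis part of the protocol summary names the number of glycaemic events among the planned superiority analyses.

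**Working it through.** **The plan's own figures.** The plan gives no figure for this comparison. Its sample sizes reproduce, n per group = 2 × (1.96 + 0.84)² × SD² / 0.4², but they do not depend on the window:
- SD 0.55: 2 × 7.85 × 0.3025 / 0.16 = 29.7, so 30.
- SD 0.8: 2 × 7.85 × 0.64 / 0.16 = 62.8, so 63.

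**Where does the study end?**

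| Points to V3 | Points to V4 |
|---|---|
| Protocol summary: follow-up is 3 months from randomisation | SAP 7.4.2: V3-V4 is listed as a period just before the total duration |
| Protocol 7.1 and 7.5: V3 is the end-of-study visit | SAP 4.1 (and Protocol 2.1): the extra month is counted in the study duration (1 + 3 + about 3 + 1 + 3 = about 11 months) |
| Protocol 7.6: V4 falls 4 weeks after the end of the study | SAP 4.4.2: safety reporting during the study, "including the additional one-month phase at the end of the study for patients in the Omnipod group" |
| SAP 7.4.1: follow-up for the primary endpoint ends at 3 months | SAP 4.4.3: V4 is used as a follow-up time |
| | Protocol 7.5: the month-4 appointment is also called end-of-study |

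The labels conflict. An analyst working from the SAP has more support for V4 than for V3.

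**Raw counts if V3-V4 is pooled by randomised arm.** Inputs: 12 weeks in both arms (SAP 4.1); the extra month taken as 4 weeks (Protocol 7.6); uptake u among Omnipod patients, not in the documents and therefore assumed.
- Mean observed weeks: Medtrum 12, Omnipod 12 + 4u.
- With equal event rates, Medtrum/Omnipod count ratio = 12 / (12 + 4u).
- u = 25%: 12/13 = 0.92. u = 50%: 12/14 = 0.86. u = 100%: 12/16 = 0.75.

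**False-positive rate of the count test.** Gamma-Poisson simulation with no true pump difference, 4,000 runs per case, two-sided 5%. There are 48 patients per arm: 100 included (SAP 5.1) minus the 4 COVID-19 discharges (SAP 7.1.3), assumed to split evenly. Mean events and between-patient CV are assumed. Entries are t-test / Mann-Whitney; Monte Carlo standard error is at most about 0.8 points.

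| Mean events per 12 weeks | CV | u = 25% | u = 50% | u = 100% |
|---|---|---|---|---|
| 40 | 0.5 | 10/9% | 28/24% | 76/71% |
| 40 | 1.0 | 6/6% | 11/9% | 29/23% |
| 40 | 1.5 | 5/5% | 7/6% | 14/11% |
| 10 | 0.75 | 8/7% | 15/12% | 40/34% |
| 10 | 1.5 | 6/6% | 8/7% | 14/11% |
| 1 | 1.0 | 5/5% | 8/8% | 16/14% |
| 0.1 | 1.0 | 5/5% | 5/5% | 6/6% |

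With no pooling (u = 0) the rate is about 4-6% in every case. In runs at 1 to 3 events per week with 50% uptake or more, nearly all significant t-tests favoured Medtrum.

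**Mean glucose over the total duration.** For an Omnipod patient who takes the extra month, 4/16 = 25% of the time is on the Medtrum pump. A time-weighted true difference therefore shrinks to 1 − 0.25u of its size: 94%, 88% and 75% at u = 25%, 50% and 100%. If the pumps do not differ, the longer window alone shifts neither mean glucose nor % time in hyperglycaemia, because both are already normalised for time.

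**The case against.** - **The text does not say that the overall count is tested.** Counts are described overall and per period, and the test sentence stands apart. Tests on V1-V2 and V2-V3 alone would fit the wording, and no between-arm test is possible in V3-V4. This stands: testing the overall count is the natural reading, not an explicit one.
- **The protocol's labels support a cut at V3.** This stands as a benign reading, and an analyst who follows it avoids the problem. It does not settle the matter, because the SAP's own wording mostly runs to V4.
- **Missing exposure adjustment matters only for raw counts.** Correct. A reader might infer that all three variables yield false positives. For mean glucose and % time in hyperglycaemia the arithmetic does not support that.
- **The large error rates need several assumptions at once.** Correct. The 76% figure needs pooling, full uptake, frequent events and a low CV together. It is not a prediction for this trial.
- **The direction assumes analysis by randomised arm.** Protocol 11.2.2 supports that for the ITT population, but SAP 7.4.2 does not define pump group. If it meant pump worn, the same patients would appear in both groups.
- **The per-period results would help to reveal a distortion.** Correct for V1-V2 and V2-V3. They do not replace a defined window for a comparison named as a superiority analysis.

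**Conclusion.** The window for the overall and total-duration comparisons in SAP 7.4.2 is undefined, and the more natural SAP reading can pool time that Omnipod-arm volunteers spend on the Medtrum pump. If that is done by randomised arm, raw hypoglycaemia counts favour Medtrum by construction (ratio 0.92 to 0.75 for uptake of 25% to 100%). The false-positive rate ranges from near 5% to well above it. Uptake, event rate and CV are assumptions throughout. For mean glucose the effect is limited to dilution of a true difference.

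A reader might infer that the planned analysis is certainly biased, or that the trial's main conclusion is at risk. The documents support neither. The bias arises only if V3-V4 is pooled. The primary endpoint, laboratory HbA1c, time in range (planned per period) and the V1-V2 and V2-V3 results are not affected. Importance is minor to moderate, but the gap should be closed before the analysis. Confidence is medium, because the test sentences do not themselves name a window.

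**What to change.** In SAP 7.4.2:
- State that every overall or total-duration variable used in a between-group comparison covers D0-V3, by randomised arm. This applies to hypoglycaemic events, mean glucose and % time in hyperglycaemia.
- Analyse hypoglycaemic events as a rate per observed sensor time, or with a count model that has an exposure offset. A cut at V3 alone is not enough: the ITTm population removes only the four COVID-19 discharges, so other early withdrawals and gaps in sensor wear still leave unequal exposure.
- Report V3-V4 separately, without a between-group test, as Medtrum exposure in former Omnipod patients.

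In SAP 4.4.2, define the evaluation period as D0-V3 for these comparisons, and reconcile the uses of follow-up and end of study in the SAP and protocol sections tabulated above.

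The cost is a few derived variables and table headers, plus observed sensor time (derivable from the FSL wear time already collected) as a denominator. No new visits or measurements are needed, and all month-4 data are still reported.

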Statistical analysis	
Data processing and statistical analysis will be carried out by the service provider, Axonal-Biostatem.
 
The statistical analyses will be described in a Statistical Analysis Plan (SAP) validated by the Sponsor and the Scientific Committee, prior to the freeze-in.
 
Statistical analyses will be performed after baseline freezing of the data with SAS® software (SAS Institute, NC, Cary, USA), version 9.4 or later.
 
Demographic and efficacy/performance analyses will be performed in the ITT population. The primary endpoint will be analyzed in PP (Per Protocol) and then validated in the ITT (intention to treat) population. The safety analyses will be performed in the safety population.
 
For quantitative variables, the usual statistics (n, missing n, mean, standard deviation (SD), median, first and third quartiles (Q1 and Q3), minimum and maximum) will be presented. IC95% may be

	
presented if relevant (especially for the primary endpoint).
 
For categorical variables, the usual statistics (n, missing n, frequency and percentage) for each modality will be provided.
 
Descriptive statistics will be provided in aggregate and by pump group.
 
The type 1 error, α, is set at 5% when the tests used will be two-sided (superiority) and α will be set at 2.5% when the tests will be one-sided in the case of Noninferiority (IC95%).
 
Analysis of the main objective
 
The non-inferiority analysis will be produced via an Ancova or mixed model on the Per-Protocol population and then on an intention-to-treat basis.
 
If non-inferiority is demonstrated, a superiority analysis will be conducted.
 
Analysis of secondary objectives
 
The secondary criteria will be described and then be the subject of mixed or Ancova models.
 
A non-inferiority analysis on HbA1c data and superiority analyses on Time in range, number of glycemic events, patient satisfaction will be performed.

Regulatory framework	ID-RCB number, CPP opinion, CNIL MR001 and RGPD compliance, information to the ANSM, approval of investigator contracts by the CNOM, transparency obligations
Logistics	CRO Axonal-Biostatem (Nanterre, France)

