4.4.3 Calculated/derived criteria

			2 = "More than 10 years
Number of years and months of treatment per pump	PUMP_D = Number of years * 12 + number of months	Time since starting pump therapy (in months)	Digital
Weight (kg) and height (cm)	BMI_D = (weight/height ²)*10000	Body Mass Index (BMI)	Digital
IMC_D	IMC4CL_D = -0 if BMI_D<18.5 -1 if BMI_D = [18,5 ; 25[-2 if BMI_D = [25; 30[. -3 if BMI_D >= 30	BMI (in classes)	0 = "Less than 18.5 1 = " [18,5 ; 25[" 2 = " [25 ; 30[" 3 = "Greater than 30
Tolerance variables	AL_PBTOL_D = -1 if the patient reported during the follow-up an irritation/itching problem or a redness problem or another adverse event -0 otherwise	Patient with at least one tolerance problem	0 = "No 1 = "Yes
HbA1c value measured in the laboratory at D0 and 3M	EVOL_HBA1C_D = HbA1c at M3 - HbA1c at D0	Evolution of HbA1c between D0 and 3M	Digital
Estimated HbA1c (FSL) (%)	EVOL_eHbA1c = HbA1c estimate at V2 - HbA1c estimate at D0 (will also be calculated for V3 and V4)	Evolution of HbA1c estimation between D0 and V2,V3,V4	Digital
Average blood glucose at different follow-up times	EVOL_GLYC_V2 = Average blood glucose at V2 - Average blood glucose at D0 (will also be calculated for V3 and V4)	Evolution of the average blood glucose level between D0 and V2, V3, V4	Digital
Average daily basal dose at different follow-up times	EVOL_BASAL_V2 = Average daily basal dose at V2 - Average daily basal dose at D0 (will also be calculated for V3 and V4)	Evolution of the average daily basal dose between D0 and V2, V3, V4	Digital
Average daily bolus dose at different follow-up times	EVOL_BOLUS_V2 = Average daily bolus dose at V2 - Average daily bolus dose at D0 (will also be calculated for V3 and V4)	Evolution of the average daily bolus dose between D0 and V2, V3, V4	Digital

Number of Boluses/day at different follow-up times	EVOL_NB_BOLUS_V2 = Number of Boluses/day at V2 - Number of Boluses/day at D0 (will also be calculated for V3 and V4)	Evolution of the number of Bolus/day between D0 and V2, V3,V4	Digital
Time of wearing the FSL	PORT_70sup = -1 wear time greater than 70%. -0 otherwise	FSL wear time greater than 70%.	0 = "No 1 = "Yes

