7.3 PATIENT CHARACTERISTICS AT INCLUSION

Inclusion parameters will be described globally and according to their group allocated by randomization on the **ITT population and then on the ITTm population**. Only demographic data will be described for **patients discharged with COVID-19**. Demographics

- Age (years)
- Gender (female; male)
- Type of diabetes (type 1; type 2)
- Time since the discovery of diabetes
- Time since discovery of diabetes (<5 years; 5-10 years; >10 years)

- Type of diabetes treatment:
 - Time since starting pump therapy (months)

Associated oral treatment

- For patients with type 2 diabetes:
 - Associated oral treatment (yes; no)
 - The list of associated oral treatments will be given via a listing

Clinical examination

- Weight (kg)
- Size (cm)
- BMI calculated (kg/m²)
- BMI calculated in classes (Lean: <18.5 kg/m²; Normal: 18.5-<25 kg/m²; Overweight: 25-<30 kg/m²; Obese: >= 30 kg/m²)
- Heart rate (bpm)
- Systolic blood pressure (mmHg)
- Diastolic blood pressure (mmHg)

Biological data

• Last HbA1c measurement in the laboratory (%)

Sensor data

- Estimated HbA1c (FSL) (%)
- FSL Wear Time (%)
- FSL wear time > 70% (yes; no)
- Average blood glucose (FSL) (mg/dl)
- Blood glucose SD (FSL) (mg/dl)
- Coefficient of variation of glucose values (%)
- Number of hypoglycemia
- Time spent in hypoglycemia <70 mg/dl (%)
- of normoglycemic values > 70-180 mg/dl (%)
- Time spent above >180 mg/dl (%)

Pump data

- Name of insulin used (Novorapid; Humalog; Apidra; Other)
 - If other, details will be given in a listing
- Average total daily insulin dose:
 - Average Daily Basal Dose
 - Average daily bolus dose
 - Number of Boluses/day

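### Hypoglycaemic events are compared as raw counts, with no exposure term, no use of the baseline count and no stated cut-off at V3

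*SAP*

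**What the plan says.** The endpoint in SAP 4.4.2 is a count: "Number of symptomatic and non-symptomatic hypoglycemic events during the evaluation period, broken down by severity level". Protocol 10.2 defines it in the same way. SAP 7.4.2 item 3 adds "The number of hypoglycemic events will be described overall and in each period by severity level", followed by "Comparisons between groups will be made using Student or Mann-Whitney tests". The analysis population is ITTm, which is ITT less the four COVID-19 discharges.

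The derived variables in SAP 4.4.3 include neither an event rate nor a change in event count. Sensor wear appears in three places:

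- SAP 4.4.3 derives a flag, "FSL wear time greater than 70" percent.
- SAP 7.4.2 item 2 says "FSL wear time (%) will be described".
- SAP 7.4.1 uses it for the primary endpoint only: "A subgroup analysis will be performed on the population of patients with an LSP wear rate >70% at M3".

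SAP 7.3 lists "Number of hypoglycemia" among the sensor data at inclusion, but no later analysis uses it.

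The protocol gives two plans. Its summary says "The secondary criteria will be described and then be the subject of mixed or Ancova models", and lists the number of glycaemic events among the superiority analyses. Protocol 11.2.4 specifies t or Mann-Whitney tests for quantitative comparisons. SAP section 6 records no modification.

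**The concern.** A sensor-detected event can be counted only while glucose is being recorded. Protocol 3.4.1 makes a complete record depend on a sensor change every 14 days and a scan at least every 8 hours. A raw count therefore combines the event rate with the time observed. Patients who leave early, other than the four COVID-19 discharges, remain in ITTm, and the SAP does not say how their counts are handled.

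The clearest exposure problem is structural. Item 2 of SAP 7.4.2 names the periods V1-V2, V2-V3 and V3-V4 and a total study duration. Item 3 then describes events overall and by period, with no end point for the overall count. Only Omnipod-arm patients have a V3-V4 period, and they spend it on the Medtrum pump. A literal total would set up to 16 weeks in one arm against 12 in the other, and would book events on the Medtrum pump to the Omnipod arm.

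This matters because both documents state the treatment goal as HbA1c control without more hypoglycaemia. More hypoglycaemia lowers mean glucose, so it could help the primary non-inferiority result. The event count is one of the places where that would show.

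**Working it through.** **1. The plan's own figures.** For the primary endpoint, n per group = 2(1.96 + 0.8416)² × SD² / margin².

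- SD 0.55, margin 0.4: 2 × 7.849 × 0.3025 / 0.16 = 29.7, so 30. Then 60 / 0.8 = 75 randomised.
- SD 0.8, margin 0.4: 2 × 7.849 × 0.64 / 0.16 = 62.8, so 63.

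Both match Protocol 11.1 and SAP 5.1. Neither document gives an event rate, dispersion or power for hypoglycaemic events, so any size quoted for this point rests on assumptions. From the documents: 100 included, less 4, gives at most 96 in ITTm, or about 48 per arm at 1:1.

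**2. What exposure alone does.** With equal true rates, the expected count ratio is the ratio of observed sensor times:

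- wear 85% versus 90%: 0.85 / 0.90 = 0.94
- wear 80% versus 90%: 0.80 / 0.90 = 0.89
- wear 70% versus 90%: 0.70 / 0.90 = 0.78
- 12 versus 16 weeks: 12 / 16 = 0.75, so the Medtrum arm would appear to have 25% fewer events

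**3. Error rate with no true difference.** Simulated trials: 48 per arm, two-sided 5%, 5,000 runs per scenario. Counts are Poisson with mean 40 × (wear × weeks / 12) × a log-normal patient effect.

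Assumed, not in the documents: 40 events per 12 weeks at full wear; between-patient variance 0.6 times the squared mean; a 4-week baseline count; 0.7 of log-scale variance shared between baseline and follow-up. The adjusted analysis is ANCOVA of log(count + 0.5 per unit sensor time) on arm and log baseline rate.

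| Exposure | Raw t | Raw Mann-Whitney | Adjusted |
|---|---|---|---|
| 85% vs 85% wear | 4.5% | 4.3% | 4.7% |
| 90% vs 85% | 6.3% | 6.6% | 5.4% |
| 90% vs 80% | 10.1% | 12.0% | 4.9% |
| 90% vs 70% | 32% | 39% | 4.7% |
| 16 vs 12 weeks, equal wear | 43% | 47% | 4.6% |

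The last row assumes that every Omnipod patient takes the optional fourth month and that it enters the total.

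**4. Power for a true rate ratio of 0.7, equal wear of 85%.**

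| Events per 12 weeks; shared variance | Raw t | Raw Mann-Whitney | Log rate, no baseline | Log rate + baseline |
|---|---|---|---|---|
| 40; 0.7 | 57% | 63% | 65% | 81% |
| 40; 0.5 | 59% | 64% | 66% | 74% |
| 40; 0.3 | 59% | 65% | 66% | 68% |
| 10; 0.7 | 51% | 53% | 53% | 61% |

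Most of the gain comes from the baseline covariate and shrinks with the baseline correlation. At a mean of 3 events, the raw and adjusted analyses differ by about one point (36% and 37%).

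**5. Choice of model.** In 1,000-run simulations, a negative binomial model with a log sensor-time offset and ordinary Wald tests rejected about 7-8% of the time under no difference. Log-rate ANCOVA held about 5%.

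**The case against.** The case for leaving the analysis alone is substantial.

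- **Exposure may well be balanced.** Both arms keep the FreeStyle Libre they already use, allocation is 1:1, and the documents report no wear imbalance. With equal exposure the raw tests are valid, and a 5-point gap costs little. A reader might infer that the plan will mistake unequal wear for a pump effect. The documents support only that it could, if wear differed.
- **There is a partial safeguard.** SAP 7.4.2 item 2 compares the percentage of values below 70 mg/dl. That measure is relative to recorded values, so wear does not scale it mechanically. Wear is also described, so an imbalance would be visible. Neither corrects the event comparison itself.
- **The SAP has not abandoned the protocol.** The protocol summary alone might suggest that a promised model was dropped. Protocol 11.2.4 specifies the tests that the SAP uses. The conflict is between the protocol's summary and its body.
- **The 20% allowance is not evidence of truncated counts.** SAP 5.1 uses it to cover deviations, missing data and loss to follow-up in the sample size.
- **Baseline adjustment is partly an efficiency preference.** Its benefit depends on a correlation the documents do not give, and the secondary objectives are framed as descriptive.
- **Sensor time is not the exposure for every event.** Events also come from patient entries in the PDM, and Level 3 is defined by clinical state. The baseline count is listed without severity levels or a stated window.

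These points limit the size of the concern and shape the remedy. They do not answer the missing cut-off at V3 or the absence of any rate.

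**Conclusion.** The point stands as a conditional weakness in a secondary analysis. The comparison is sound if sensor time and follow-up are equal between arms; otherwise the count difference partly reflects exposure. Under the assumed rates the error is about 6-7% for a 5-point wear gap, 10-12% for a 10-point gap, and 43-47% if the Omnipod-only fourth month enters a 16-versus-12-week total. That last case rests on a gap in the SAP's wording and can be closed with one sentence. The cost in power is real when events are frequent and baseline is predictive, and small when events are sparse. The error and power figures depend on the assumed event rate, dispersion and baseline correlation. The primary non-inferiority conclusion is unaffected.

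**What to change.** In SAP 7.4.2 item 3:

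1. Restrict the between-arm comparison to V1-V3. Report V3-V4 descriptively, by the pump in use.
2. Analyse sensor-detected events per observed sensor time, taken as FSL wear percentage times days in the window. Adjust for the total baseline hypoglycaemia rate, and state the baseline window.
3. Use log-rate ANCOVA with a pre-set rule for zero counts, or negative binomial regression with a log sensor-time offset and robust standard errors. Report a rate ratio with its 95% confidence interval.
4. Keep Mann-Whitney on rates as a sensitivity analysis and for sparse severity levels.
5. List Level 3 and PDM-entered events separately.
6. Reconcile the protocol summary with Protocol 11.2.4, and record the change in SAP section 6.

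Wear percentage and the baseline count are already planned variables. The cost is slightly more analysis work and a result a little harder to present than a rank test.
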